3.9.3. Troponin Evaluation and Stopping Criteria

If post-screening, the local cTn is >Institutional ULN it is recommended that subjects undergo urgent evaluation of cardiac ischemia symptoms and ECG should be performed to rule out cardiac ischemia. An urgent repeat of cTn value and collection of sample for central lab evaluation should be obtained within 24 hours.

Asymptomatic subject:

If the second value of cTn is \leq ULN the subject can continue on study with close follow up of symptoms, ECG, and further cTn measurements as clinically indicated

If the second value of cTn remains >ULN treatment with GSK2857916 should be interrupted. The subject should undergo cardiac evaluation including ECHO testing for cardiac function. Any re-start of study treatment must be discussed with the GSK medical monitor who will consult with a member of the internal cardiotoxicity panel prior to re-start.

If the second value of cTn exceeds the threshold for MI according to local lab parameters, obtain cardiology consultation immediately. Permanently discontinue GSK2857916 and withdraw the subject from the study.

Symptomatic subject:

Obtain cardiology consultation immediately. Permanently discontinue GSK2857916 and withdraw the subject from the study.

3.9.4. Left Ventricular Ejection Fraction (LVEF)

3.9.4.1. LVEF Stopping Criteria

Echocardiography (ECHO) must be performed at Screening and as outlined in the Time and Events Tables (Section 7.1). Subjects who have an asymptomatic, absolute decrease of >15% in LVEF compared with baseline or an absolute decrease of >10% in LVEF compared with baseline and the ejection fraction is below 50% should temporarily interrupt GSK2857916 and have a repeat evaluation of LVEF within 1 week. ECHO should be repeated every 1 to 2 weeks for 4 weeks or until LVEF recovery to within 15% of baseline or to above 50% and within 10% of baseline depending on which stopping criteria above were met.

- If the LVEF recovers (defined as absolute decrease $\leq 15\%$ compared to baseline or $\geq 50\%$ and absolute decrease $\leq 10\%$ compared with baseline) at any time during the next 4 weeks, after consultation and approval of the GSK Medical Monitor, the subject may be restarted on GSK2857916 at a reduced dose. For such subjects, monitoring of LVEF will be performed 2, 4, and 8 weeks after rechallenge, and then per protocol
- If LVEF does not recover within 4 weeks, treatment with GSK2857916 should be permanently discontinued. Ejection fraction should be monitored every 4 weeks for a total of 16 weeks or until resolution

Subjects with Grade 3 or 4 symptomatic left ventricular systolic dysfunction must discontinue treatment with GSK2857916. Ejection fraction should be monitored every 4 weeks for a total of 16 weeks or until resolution.

Copies of all ECHOs and cardiology consultations performed on subjects who experience a $>15\%$ decrease in LVEF from baseline or $>10\%$ decrease in LVEF from baseline and whose cardiac ejection fraction is $<50\%$ will require review by a GSK medical monitor. Instructions for submitting qualifying ECHOs/MUGAs are provided in the SPM.

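### The LVEF restart rule drops the qualifier that ties recovery to the criterion met, so below a 65% baseline a subject can count as recovered while still meeting an interruption criterion

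*Protocol*

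**What the plan says.** All the relevant text is in Protocol section 3.9.4.1, LVEF Stopping Criteria.

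- **Interruption, criterion 1:** "Subjects who have an asymptomatic, absolute decrease of >15% in LVEF compared with baseline".
- **Interruption, criterion 2:** a fall of more than 10 points "in LVEF compared with baseline and the ejection fraction is below 50% should temporarily interrupt GSK2857916".
- **Repeat ECHOs:** these continue for 4 weeks or until "recovery to within 15% of baseline or to above 50% and within 10% of baseline depending on which stopping criteria above were met".
- **Restart bullet:** it opens "If the LVEF recovers (defined as absolute decrease" and accepts either a fall of no more than 15 points, or LVEF of at least 50% with a fall of no more than 10 points. The two limbs are joined by a plain 'or'. A subject who recovers within the 4 weeks may resume: "after consultation and approval of the GSK Medical Monitor, the subject may be restarted on GSK2857916 at a reduced dose".
- **Discontinuation bullet:** "If LVEF does not recover within 4 weeks, treatment with GSK2857916 should be permanently discontinued".
- **Safeguards:** after restart, "monitoring of LVEF will be performed 2, 4, and 8 weeks after rechallenge". The ECHOs of subjects crossing either threshold "will require review by a GSK medical monitor".

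Table 14 in section 5.2.1 requires LVEF of at least 50% at entry.

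**The concern.** The section states the recovery rule twice, and the two statements differ. The first, which sets how long ECHOs are repeated, makes the target depend on the criterion that was met. The second, which is the express definition for restart, does not. A limb that can never change the outcome suggests that the qualifier was lost in drafting.

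The word defined in the restart bullet drives two dosing decisions: whether a subject may resume, and whether treatment ends permanently at 4 weeks. Taken at its word, the bullet lets a subject interrupted under criterion 2 qualify for restart with that criterion still met. It also means that a subject who stays at a fall of 11 to 15 points with LVEF below 50% would not trigger permanent discontinuation.

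**Working it through.** The plan gives no figure to reproduce; this is a check of the logic. Let B be baseline LVEF (at least 50, Table 14) and E a later value, both in percentage points.

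- C1 (interrupt): B − E > 15
- C2 (interrupt): B − E > 10 and E < 50
- L1 (first recovery limb): B − E ≤ 15
- L2 (second recovery limb): E ≥ 50 and B − E ≤ 10
- Restart bullet as written: L1 or L2

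**Step 1: is the second limb redundant?** L2 requires B − E ≤ 10, which implies B − E ≤ 15, so L2 implies L1. On a 0.5-point grid (B from 50 to 80, E from 20 up to B) none of 5,551 combinations satisfies L2 without L1. As written, recovery is simply a fall of 15 points or less.

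**Step 2: when does a literally recovered value still meet C2?** This needs 10 < B − E ≤ 15 and E < 50, that is, B − 15 ≤ E < min(B − 10, 50). A solution exists only if B − 15 < 50, so B < 65. In whole numbers:

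| Baseline | Values recovered with C2 still met | Count |
|---|---|---|
| 50 | 35–39 | 5 |
| 55 | 40–44 | 5 |
| 60 | 45–49 | 5 |
| 61 | 46–49 | 4 |
| 62 | 47–49 | 3 |
| 63 | 48–49 | 2 |
| 64 | 49 | 1 |
| 65 and above | none | 0 |

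The count is 5 at each of the 11 baselines from 50 to 60, so the total is 11 × 5 + 4 + 3 + 2 + 1 = 65. These are LVEF values, not subjects. They are exactly the values that meet C2 without C1, because C2 without C1 is also 10 < B − E ≤ 15 with E < 50.

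**Step 3: examples.**

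- Baseline 60, LVEF 48: the fall is 12, so C2 is met and C1 is not. L1 already holds at the ECHO that triggered the interruption.
- Baseline 62, LVEF 45: the fall is 17, so both criteria are met. If LVEF rises to 48 the fall is 14. L1 holds, and so does C2.

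**Step 4: when should L1 govern alone?** Only for a subject who met C1 without C2, which needs E ≥ 50 and E < B − 15, hence B > 65. In whole numbers the first such value appears at baseline 66 (E = 50); at baseline 70 there are five (50–54). At baselines 50 to 65 every fall of more than 15 points leaves LVEF below 50, so C2 is met too.

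**Step 5: test the repair.** Require L2 if C2 was met at interruption, and L1 if only C1 was met.

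- L2 excludes C1 (the fall is at most 10) and C2 (E is at least 50).
- With C1 alone, B > 65, so L1 gives E ≥ B − 15 > 50, which excludes C2.

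No recovered value then meets an interruption criterion at any baseline.

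A simpler rule, recovered when neither criterion is met, would be looser than the existing second limb. At baseline 50 it would accept 40–49, and at baseline 65 it would accept 50–54.

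**The case against.** The best reply is that the sentence just before the bullet already supplies the rule. The bullet repeats the same two limbs in the same order, and nothing in it revokes the qualifier. A reading that empties one limb, contradicts the preceding sentence and calls a subject recovered at the triggering ECHO is a reading a careful investigator would reject. The first example is also weaker than the second, because the bullet speaks of recovery during the following 4 weeks and a repeat ECHO is due within 1 week. The qualifier refers to criteria in the plural, so it can fairly be taken to make a subject who met both clear both. Restart is discretionary and needs Medical Monitor approval, and the ECHO review sentence restates both thresholds for whoever does the review.

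Most of this stands as evidence of intent and as a limit on harm. It does not make the two statements agree. The qualified sentence governs how long ECHOs are repeated; the bullet holds the definition on which restart and permanent discontinuation turn. The second example survives the timing point. The case of a subject who met both criteria, which at baselines 50 to 65% is every subject with a fall of more than 15 points, is nowhere spelled out. The person approving a restart also needs a correct threshold to apply.

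**Conclusion.** The point holds, at minor severity. As written, the recovery definition conflicts with the sentence before it and gives the wrong answer for subjects interrupted under the 10-point criterion. The affected range is eligible baselines from 50% to below 65%, with up to five whole-number LVEF values at each. How many subjects this would touch cannot be estimated, because the protocol gives no frequency of LVEF falls.

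The conclusion rests on reading the bullet literally and on treating the percentages as absolute points, as the section itself does. If the qualifier is carried forward, subjects who met one criterion are handled correctly, and those who met both go most naturally to the stricter limb. No endpoint or analysis depends on this rule.

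**What to change.** In the restart bullet of section 3.9.4.1, state that a subject who met the criterion of a fall of more than 10 points with LVEF below 50%, alone or together with the 15-point criterion, has recovered only when LVEF is at least 50% and the fall is 10 points or less. State that the limb of a fall of 15 points or less applies only to subjects who met the 15-point criterion alone.

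As a tidy-up with no effect on dosing, align the repeat-ECHO sentence, which asks for LVEF above 50%, with the bullet's at least 50%.

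The cost is one sentence in an amendment, with no new assessment.

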3.9.4.2. Valvular Toxicity Stopping Criteria

Subjects who develop a new asymptomatic, moderate regurgitation or stenosis by echocardiogram (ECHO) (Grade 2 mitral/tricuspid/aortic valvular toxicity per National Cancer Institute- Common Toxicity Criteria for Adverse Events [NCI-CTCAE], version 4.0) should temporarily discontinue GSK2857916 and have a repeat evaluation by ECHO within 1 week. ECHO should be repeated every 1 to 2 weeks for 4 weeks or until valve recovery to baseline.

- If the valve recovers to baseline any time during the next 4 weeks after consultation and approval of the GSK Medical Monitor, the subject may be restarted on GSK2857916 at a reduced dose(s). For such subjects, monitoring of the valve via ECHO will then be performed 2 and 4 weeks after rechallenge, and every 4 weeks thereafter for 8 weeks and then per protocol.
- If repeat ECHO does not reveal valve recovery to baseline within 4 weeks, then the subject should permanently discontinue GSK2857916. The valve should continue to be monitored via ECHO every 4 weeks for 8 weeks or until resolution.

Subjects with a Grade 3 or 4 (symptomatic, severe regurgitation/stenosis by imaging with symptoms controlled by medical intervention) valvular toxicity must discontinue GSK2857916. Valvular toxicity should continue to be monitored every 4 weeks for 12 weeks or until resolution. If recovery occurs (return to baseline via imaging AND symptom resolution) within 4 weeks, the subject may restart GSK2857916 at a reduced dose after consultation and approval of the GSK Medical Monitor.

ECHO must be performed at baseline and at the final study visit. Copies of all ECHO(s) and cardiology consultations performed on subjects who experience valvular toxicity will

be required by GSK for review. Instructions for submitting qualifying ECHOs are provided in the Study Procedures Manual (SPM).

3.9.5. Infusion-related Reactions and Cytokine Release Syndrome

Premedication is not allowed prior to first infusion unless deemed medically appropriate by the GSK Medical Monitor in consultation with investigators following evaluation of infusion related reactions across cohorts. Premedication should be considered in any subject who experienced an infusion related reaction at first or any subsequent infusion with GSK2857916.

If an infusion-related reaction occurs during administration, the infusion rate may be reduced or halted at the discretion of the investigator and/or GSK medical monitor depending on the severity of the symptoms. The subject will receive appropriate medical treatment. When the subject's condition is stable, the infusion may be restarted according to the judgment of the investigator. Upon restart, the infusion rate should be half of the infusion rate at the time the infusion was paused.

Blood for serum cytokines should be collected in each subject who developed infusion related reaction regardless whether the infusion has been completed or not. The time of serum collection will be documented in eCRF.

- Grade 1 allergic reactions or cytokine release syndrome
 - If infusion is ongoing, it may continue but subject should be monitored carefully to ensure that ongoing signs and symptoms do not progress and worsen warranting intervention as described below
- Grade 2 allergic reactions and/or cytokine release syndrome
 - Stop the infusion, follow subject frequently for clinical symptoms
 - Initiate symptoms treatment as clinically indicated
 - Once subject has recovered to baseline and if in the opinion of the investigator the safety/risk benefit is favorable, consideration can be given to restarting the infusion at 50% of the original rate after pre-medication with H1 receptor antagonist and acetaminophen
 - If treatment is continued, the subject should be pre-medicated prior to each subsequent dose and the infusion will be administered at 50% of the original rate
- Grade 3 or higher allergic reactions and/or cytokine release syndrome
 - Stop infusion immediately
 - Initiate symptoms treatment as clinically indicated
 - Do not resume infusion with GSK2857916

- Follow the subjects for safety as clinically indicated until toxicity resolves
- Complete safety documentation
- Subjects who experience \geq Grade 3 allergic reaction will be withdrawn from study
- Further treatment with GSK2857916 in subjects who experience a \geq Grade 3 infusion related reaction needs to be discussed with MM prior to next dose administration. Those subjects will be allowed to continue on study after recovery of the reaction to \leq Grade 1 but will have to receive pre-medication prior to each subsequent dose of GSK2857916, and their infusion time will be extended to 2-4 hours (depending on severity of the reaction).

3.9.6. Allergic and Anaphylactic reaction

As GSK2857916 is a fully humanized ADC, it is considered unlikely for acute allergic reactions to occur in response to GSK2857916 exposure; however, all subjects will be monitored carefully for evidence of allergic response. A subject that exhibits signs or symptoms of severe hypersensitivity or anaphylaxis will receive appropriate medical treatment and be withdrawn from the study.

In accordance with the preparedness for treatment of anaphylaxis, emergency resuscitation equipment, advanced cardiac life support equipment, and medications must be readily accessible during GSK2857916 administration.

It is important to recognize early signs of an anaphylaxis reaction and appropriate treatment must begin immediately to prevent progression to severe anaphylaxis. Subjects will be closely monitored in an appropriate setting for early signs of dyspnea and edema. Antihistamines, such as diphenhydramine; and corticosteroids such as prednisone may be given to reduce symptoms.

If more severe clinical signs arise, immediate assessment of the ABC's (airway, breathing, and circulation from Basic Life Support) will be done in all suspected anaphylactic reactions. Cardio-Pulmonary Resuscitation (CPR) will be initiated if needed. Epinephrine will be given by injection without delay. Emergency interventions may include endotracheal intubation or tracheostomy. Treatment for shock will include IV fluids and medications that support the actions of the heart and circulatory system.

3.9.7. Tumor Lysis Syndrome (TLS) Prevention and Treatment Recommendations

Subjects with a high tumor burden with a high proliferative rate might be at risk for TLS and should be monitored for clinical and laboratory signs of tumor lysis. Specifically, all subjects with elevated uric acid ($>8\text{mg/dL}$, or $>476\text{mmol/L}$) should receive prophylaxis with allopurinol, or rasburicase. All subjects should be hydrated to reduce risks for renal toxicity and tumor lysis syndrome (TLS) with GSK2857916 treatment. Adequate fluid volume status should be maintained throughout treatment and blood chemistries should

be monitored as indicated in the Time and Events Tables in Section 7.1 or more frequently if clinically indicated. Prior to the first dose in Cycle 1, all subjects should receive at least 250- 500 mL of intravenous normal saline or other appropriate intravenous fluid. Additionally, 250-500 mL of intravenous fluid should be given as needed following GSK2857916 administration. Intravenous hydration should be continued, as needed, in subsequent cycles and subjects should be monitored for fluid overload during this period.

If the constellation of clinical and/or laboratory signs tested on Cycle 2 Day 1 indicates a possibility of developing TLS, subjects should be hospitalized with frequent monitoring of clinical signs and clinical chemistries and treated accordingly.

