3.3.3. Dose-Limiting Toxicity - Part 1 only

Any subject in Part 1 (Dose Escalation) who received at least one dose of the drug (regardless of schedule) will be evaluated for DLTs. Safety data together with DLTs will be reviewed during the dose escalation meetings prior to opening enrollment into subsequent cohorts (see Section 12.1).

Subjects who have been withdrawn from the study for reasons other than toxicity but prior to completion of DLT observation period will be replaced. An event will be considered a DLT if its relationship to the investigational agent cannot be ruled out occurs within the DLT reporting period (first 21 days of treatment for schedule 1, and first 28 days for schedule 2) and meets one of the following criteria:

- Albuminuria ≥ 2000 mg/24 hr which has been confirmed by repeat test at least 7 days apart and is not considered to be related to disease progression based on consultation of investigator with GSK medical monitor
- Grade 4 neutropenia (without fever) lasting ≥ 7 days
- Febrile neutropenia lasting ≥ 72 hours
- Grade ≥ 3 thrombocytopenia associated with bleeding where estimated blood loss is > 10 mL or Grade 4 thrombocytopenia lasting > 7 days and not responding to platelet transfusions
- Any Grade 3 or greater non-hematologic toxicity as described in Common National Cancer Institute-Terminology Criteria for Adverse Events (NCI-CTCAE) version 4.0 [NCI, 2009] with the exception of the following Grade 3 events that can be controlled within 48 hours with routine supportive measures
 - Nausea and vomiting that can be controlled with anti-emetics
 - Diarrhea that can be controlled with anti-diarrheals
 - Rash or other skin reactions that can be controlled with antihistamines and steroids
 - Clinically asymptomatic electrolyte abnormalities which can be corrected within 48 hours)
- Liver toxicity meeting pre-specified GSK liver stopping criteria (see Liver in Section 3.9.1)

Tumor lysis syndrome does NOT constitute a DLT (Section 3.9.7).

A subject who develops a DLT will be allowed to stay on study only if the toxicity did not meet stopping criteria and recovered to \leq Grade 1 within 14 days, or after a longer recovery time if benefit to subject can be demonstrated and if the investigator and medical monitor agree that for a given subject the benefits may outweigh the risks.

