10.1. Permitted Medication(s)

Subjects should receive full supportive care during the study, including transfusion of blood and blood products, growth factors, and treatment with antibiotics, anti-emetics, antidiarrheals, and analgesics, as appropriate.

Steroids are not allowed unless used for pre-medication prior to GSK2857916 infusion.

Concomitant therapy with biphosphonates is allowed.

Concomitant prophylactic treatment for tumor lysis syndrome (according to local standards) in subjects with high tumor load, where TLS may occur is permitted and should be considered.

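### Section 3.9.7 gives two uric acid limits that differ 1000-fold, and ties hospitalisation for possible tumor lysis to Cycle 2 Day 1, which does not match the Cycle 1 chemistry schedule

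*Protocol*

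**What the plan says.** Protocol section 3.9.7 contains three relevant instructions.

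- **Prophylaxis.** "all subjects with elevated uric acid ($>8\text{mg/dL}$, or $>476\text{mmol/L}$) should receive prophylaxis with allopurinol, or rasburicase". The sentence is not tied to any visit.
- **Hospitalisation.** "If the constellation of clinical and/or laboratory signs tested on Cycle 2 Day 1 indicates a possibility of developing TLS, subjects should be hospitalized". The rest of that sentence covers closer observation and treatment in hospital. No other visit is named.
- **General precautions.** All subjects receive intravenous fluid before the first Cycle 1 dose, and blood chemistries are to "be monitored as indicated in the Time and Events Tables in Section 7.1 or more frequently if clinically indicated".

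Table 15 (section 7.3.7) lists uric acid within the clinical chemistry panel. The Part 1 tables (7.1.1.1 and 7.1.1.2) mark that panel on Cycle 1 Days 1, 2, 8 and 15. The four Part 2 tables (7.1.2.1 to 7.1.2.4) mark it on Cycle 1 Days 1, 8 and 15. The Day 1 test may be omitted if it was done within 72 hours before the first dose.

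**The concern.** A decision limit printed in two units should mean the same thing in both, because a site will use the unit its laboratory reports. Here one of the two cannot be reached by any subject, so a site that took the SI figure at face value would give no prophylaxis under it.

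The hospitalisation sentence raises a separate question. It acts on results from a visit three or four weeks after the first dose, while the same section arranges hydration around that first dose and the tables collect chemistry throughout Cycle 1. In Part 1 the tables add a Day 2 chemistry draw without a matching hematology or INR/PTT draw, and the hospitalisation sentence does not mention it. What is at stake is clear and uniform safety instructions in a first-in-human study. No endpoint or error rate is involved.

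**Working it through.** **Uric acid limit**

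Inputs: 8 mg/dL and 476 mmol/L (section 3.9.7); molar mass of uric acid 168.11 g/mol (assumed physical constant, not in the protocol).

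Formula: mmol/L = mg/dL × 10 / molar mass.

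1. 8 mg/dL: 8 × 10 / 168.11 = 0.4759 mmol/L = 475.9 µmol/L. The printed number 476 is reproduced in µmol/L but not in the printed unit, mmol/L.
2. In reverse: 476 × 168.11 / 10 = 8,002 mg/dL.
3. Ratio: 8,002 / 8 = 1000.
4. Sensitivity: a molar mass of 168.0 gives 476.2 µmol/L and 168.2 gives 475.6 µmol/L, so the assumption does not matter.

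**Could the micro sign have been lost in reading the PDF?**

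The creatinine figures allow a check, using the factor 88.4 from Appendix 9.

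- Section 3.10.2 pairs 0.3 mg/dL with 26 µmol/L (0.3 × 88.4 = 26.5) and 0.5 mg/dL with 44 µmol/L (0.5 × 88.4 = 44.2). The micro sign prints correctly there.
- Appendix 1 pairs a rise of 2 mg/dL with 177 mol/L (2 × 88.4 = 176.8, so µmol/L is meant). The micro sign is missing there.

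A reading fault in section 3.9.7 is therefore possible but not shown.

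**Timing of the hospitalisation check**

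| Schedule | Cycle length | Cycle 2 Day 1 | Cycle 1 doses on | Days since last dose |
|---|---|---|---|---|
| 1 | 21 days | 21 + 1 = Day 22 | Day 1 | 22 − 1 = 21 |
| 2 | 28 days | 28 + 1 = Day 29 | Days 1, 8, 15 | 29 − 15 = 14 |

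Footnote 1 of the tables places dosing-day assessments before drug administration unless otherwise specified, so the Cycle 2 Day 1 chemistry precedes that day's dose. The scheduled Cycle 1 chemistry points before it number four in Part 1 (Days 1, 2, 8, 15) and three in Part 2 (Days 1, 8, 15). The first one scheduled after a dose is Day 2 in Part 1 and Day 8 in Part 2. The hospitalisation sentence refers to none of them.

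**The case against.** The strongest reply is that little in practice depends on either defect, and much of that stands.

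- **The mg/dL limit works.** The two limits are joined by an or, so a result above 8 mg/dL at any visit calls for prophylaxis. The digits 476 are right for µmol/L, and many readers would recognise the slip. The protocol does not say which units any site reports, so a difference in prophylaxis between sites cannot be asserted.
- **Other precautions remain.** Hydration of all subjects before the first dose and extra chemistry when clinically indicated depend on neither sentence. The Cycle 2 Day 1 sentence does not forbid earlier hospitalisation.

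Several stronger readings are tempting, but the protocol does not support them.

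- *Neither TLS safeguard works.* The mg/dL limit works, and the hospitalisation rule operates at the visit it names.
- *No action attaches to the Day 2 chemistry.* A uric acid result above 8 mg/dL on that draw triggers prophylaxis like any other.
- *Cycle 2 Day 1 is a transposition of Cycle 1 Day 2.* This is plausible but unproven, and Part 2 has no Day 2 visit.
- *Section 10.1 conflicts.* It says prophylaxis "in subjects with high tumor load, where TLS may occur is permitted and should be considered". That is a different trigger, and both statements can apply together.
- *The DLT exclusion hides failures.* Section 3.3.3 does say "Tumor lysis syndrome does NOT constitute a DLT", but sections 3.3.1.1, 3.3.1.2.1 and 12.1 have escalation decisions review all available safety data, so TLS events would still be seen.

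**Conclusion.** Two points hold.

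1. As printed, the SI uric acid limit is 1000 times the mg/dL limit it is paired with. This rests only on the molar mass of uric acid and on the unit having been read correctly from the PDF. The consequence is conditional: it arises only where a site applies the SI figure literally.
2. The hospitalisation sentence names a single visit, Day 22 or Day 29, which does not match the Cycle 1 chemistry schedule in either Part.

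Both are defects in the wording of a safety section and call for a clarification of modest severity. Sample size, type I error and power are unaffected. The documents do not show that TLS protection as a whole fails.

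**What to change.** Check the SI unit in section 3.9.7 against the source document and, if it is printed as read here, correct it so that both units state the same limit. Have the sponsor reconcile the Cycle 2 Day 1 sentence with the Time and Events tables, separately for Part 1 and Part 2, and state which scheduled results the hospitalisation instruction uses. The choice of visit and of clinical rule is the sponsor's. The cost is a text correction in an amendment and a letter to sites, with no added visit or sample.
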